# 4.10 Study Outcome Measures and Ascertainment

#### 4.10.1 Primary Outcome

- 1. Pathogenic, likely pathogenic, or VUS variants identified by sequencing and deemed reportable by the Variant Adjudication Committee
- 2. Maternal hospital charges between time of presentation to hospital for delivery to discharge, and neonatal hospital charges between delivery and infant discharge or death

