#### 4.10.2 Secondary Outcomes (Prenatal sequencing and unsequenced prenatal)

- 1. Perinatal outcomes including gestational age at delivery, major morbidities including mechanical ventilation, sepsis, pressor support, ECMO, metabolic abnormalities (e.g., acidosis, elevated uric acid, hypo-/hyperglycemia), intraventricular hemorrhage, periventricular leukomalacia, encephalopathy, and seizure
- 2. Neonatal/infant death at time of discharge and at 12 months of age\*
- 3. Length of initial NICU stay and number of days spent in the hospital between initial discharge and 12 months of age\*
- 4. Infant weight and length at 12 months of age\*

- 5. Developmental parameters (communication, gross motor, fine motor, problem solving and personal-social) at 12 months of age using ASQ-3\*
- 6. Anxiety following result disclosure (or 4 weeks post enrollment for the unsequenced group), neonatal discharge and 12 months postpartum\*
- 7. Depression following result disclosure (or 4 weeks post enrollment for the unsequenced group), neonatal discharge and 12 months postpartum\*
- 8. Quality of life for the patient and family at 12 months postpartum\*
- 9. Incremental cost per Quality Adjusted Life Year (QALY)
- \* Only available on participants enrolled prospectively and followed through 12 months postpartum

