#### 5 Statistical Considerations

# 5.1 Power and sample size

The first primary outcome for this study is the frequency of pathogenic, likely pathogenic, or VUS genomic variants identified by sequencing among participants with a normal karyotype and CMA. The sample size is based on the incremental yield reported in a prospective study of WES performed at Columbia University in a similar population. Among 234 parent-fetus trios without CMA abnormalities, a genetic diagnosis was reported in 22 (9.4%). The precision of the estimate for a range of sample sizes and estimates is shown in Table 4. An estimate of 9.4% and sample size of 750 in the prenatal sequenced group will have a precision of 2.3% (confidence interval half-width) with a 93% probability.

Estimate	Sample size	Cl ½-width
9.0%	700	2.4%
	750	2.3%
	800	2.2%
9.4%	700	2.4%
	750	2.3%
	800	2.3%
9.8%	700	2.5%
	750	2.4%
	800	2.3%

The second primary outcome is maternal and neonatal hospital charges. The utilization of health care and cost only will include women that deliver at one of the study centers. Given that some of the recruiting centers include referrals in which the women will not deliver at the study center, power estimates assume cost will be available on 500 of the 750 in the prenatal sequencing group. Similarly, of the 350 unsequenced prenatal controls, 15% are assumed to have a pathogenic or likely pathogenic causal pre-/postnatal CMA prior to neonatal discharge or deliver elsewhere resulting in approximately 300 unsequenced prenatal controls available for analysis. The total charges for deliveries at Columbia University that required a NICU admission in 2016 and 2017 (partial year) were used to provide cost estimates. The charges follow a lognormal distribution approximately with a mean total charge of \$277,902 and standard deviation of \$389,484. Assuming 500 participants in the prenatal WGS group, and 300 unsequenced prenatal control participants, the study will have 80% power to detect a mean ratio of 0.80 (20% reduction) with an alpha=0.05 two-sided.

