## 5.3 Prenatal Sequencing and Prenatal Unsequenced Groups

Clinical management including health care utilization and cost, and pregnancy and neonatal outcomes will be compared among the prenatal sequencing group and the unsequenced prenatal group (prospective and retrospective). Women whose fetus or neonate is found to have pathogenic or likely pathogenic causal findings on CMA prior to neonatal discharge will be excluded from these analyses. Twelve month postpartum outcomes will be compared only among those individuals enrolled prospectively. Initially, demographic data and severity of ultrasound findings will be compared to ensure there are no significant differences between the two study groups (prenatal sequencing and unsequenced prenatal group). If differences are found, the covariates will be adjusted for in the analyses.

Categorical variables will be reported as the number and frequency and associations assessed by the Pearson's chi-square or Fisher's Exact test. The distributions for continuous variables will be assessed for normality and transformed to fit a normal distribution if possible. Normal distributions will be reported as mean and standard deviation and compared with the t-test, and non-normal data will be reported as median and interquartile range and compared with the Mann-Whitney U test.

For each outcome, if the study groups show a significant difference, interactions will be tested and subgroup analyses conducted if the interaction is significant (p<0.05). Pre-specified subgroup analyses include maternal age, race/ethnicity, fetal sex, and type of anomaly (lethal vs non-lethal).

The amount of missing data, missing data patterns, and identification of variables associated with missingness will be explored to inform the primary and sensitivity statistical analyses. Analytic techniques used to address missing data bias will be used as appropriate. A two-sided nominal p-value less than 0.05 will indicate statistical significance.

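### NICU stay has no rule for infants who die and neonatal charges stop at death, so excess early deaths in one group can read as a shorter, cheaper stay

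*Combined protocol and SAP*

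**What the plan says.** All references are to the current protocol (version 1.8).

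- **NICU stay.** Section 4.10.2 lists "Length of initial NICU stay and number of days spent in the hospital between initial discharge and 12 months of age". Death at discharge is a separate outcome in the same list. Nothing says what stay is assigned to an infant who dies before discharge.
- **Charges.** Section 4.10.1 makes hospital charges the second primary outcome. The maternal part runs from presentation for delivery to discharge; the infant's part is "neonatal hospital charges between delivery and infant discharge or death".
- **Who is in the cost set.** Section 5.1: "The utilization of health care and cost only will include women that deliver at one of the study centers". The next sentence explains this by referrals who deliver elsewhere.
- **Test.** Section 5.3 transforms continuous outcomes and uses a t-test where possible; otherwise "non-normal data will be reported as median and interquartile range and compared with the Mann-Whitney U test". Sections 5.1, 5.3 and 5.3.1 contain no ranking of death, competing-event analysis, survivor analysis or rule for pregnancies that end in loss. The missing-data paragraph is generic.
- **Losses are foreseen.** Section 4.7 times a survey from fetal demise or termination. Section 3.2.1.2 excludes only planned termination or existing demise, so a termination decided after a result remains in the enrolled sequenced group. Section 3.2.3.2 excludes retrospective controls with a loss within 3 weeks of diagnosis; the sequenced group has no matching rule for losses after enrollment.

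**The concern.** Both outcomes are read as smaller is better, and death shortens both. Background section 2.2.3 names redirection of care among the changes that follow a genetic diagnosis. If a prenatal diagnosis leads to less intensive care and earlier death in some infants, their NICU days and charges fall. The group comparison then moves in the direction of benefit even if care of survivors is identical. Reporting death in another row does not alter the stay or charge test.

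Charges are a primary outcome, and section 5.3.1 labels a cost-benefit ratio below 1 as cost saving. A reader of a significant reduction could not tell more efficient care from early death. Terminations add a second ambiguity: under a delivery-based charge window it is unclear whether they carry maternal charges only or fall out of the comparison.

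**Working it through.** **1. The plan's own power figure.** Inputs from section 5.1: "mean total charge of \$277,902 and standard deviation of \$389,484"; 500 sequenced and about 300 unsequenced.

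- CV = 389,484 / 277,902 = 1.40. Log-scale SD = sqrt(ln(1 + 1.40²)) = 1.042.
- SE = 1.042 × sqrt(1/300 + 1/500) = 0.0761. |ln 0.80| / SE = 0.2231 / 0.0761 = 2.93.
- Power = Φ(2.93 − 1.96) = 83%; with Mann-Whitney efficiency 3/π, 82%.

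The stated 80% is reproduced and slightly conservative. It does not address death or termination.

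**2. NICU stay, no effect on care.** Assumptions, none from the documents except the group sizes: lognormal stays with log SD 1; median 21 days in survivors and 4 days in infants who die; control mortality 10%; 500 vs 300; 2,000 simulated trials per scenario; Mann-Whitney at two-sided 5%. The second column is the share of trials that find a significantly shorter stay in the sequenced group.

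| Mortality, sequenced vs control | False shorter stay |
|---|---|
| 10% vs 10% | 2.5% (nominal) |
| 11-12% vs 10% | about 3-6% |
| 15% vs 10% | about 15% |
| 15% vs 10%, deaths at median 10 days | about 7% |

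Plausibility: section 5.1 plans on 9.4% diagnosed. A 5-point excess means 5 / 9.4 = 53% of all diagnosed infants dying additionally, so it is already an extreme case. An excess above 9.4 points cannot arise from diagnosed cases alone.

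**3. Charges, no effect on care.** The section 5.1 lognormal is used. A share d of the sequenced group dies early at a fraction f of its usual charge (d and f are assumptions). Arithmetic mean ratio = 1 − d(1 − f); geometric mean ratio = exp(d ln f).

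| d | f | Arithmetic | Geometric | False saving, log t-test | False saving, Mann-Whitney |
|---|---|---|---|---|---|
| 2% | 0.1 | 0.98 | 0.955 | 8% | 7% |
| 5% | 0.1 | 0.955 | 0.89 | 27% | 17% |
| 9.4% | 0.1 | 0.915 | 0.805 | 73% | 52% |
| 2% | 0.5 | 0.99 | 0.986 | 3% | 3% |
| 5% | 0.5 | 0.975 | 0.966 | 6% | 6% |
| 9.4% | 0.5 | 0.953 | 0.937 | 14% | 12% |

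The 9.4% rows are ceilings: every diagnosed infant would have to die early. Even at f = 0 the arithmetic mean could fall by no more than 9.4%, short of the 20% target. The log-scale test reacts more strongly because it weights very low charges heavily.

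**4. Terminations left out.** If a share p of the sequenced group terminates and would have had m times the average charge, the mean of those who remain changes by (1 − pm)/(1 − p). Assume 30-50% of the 9.4% terminate, so p = 0.028-0.047.

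- p = 0.028, m = 1.5: (1 − 0.042)/0.972 = 0.986.
- p = 0.047, m = 3: (1 − 0.141)/0.953 = 0.901.
- p = 0.047, m = 0.5: (1 − 0.0235)/0.953 = 1.025.

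The direction depends on m, which the documents do not give.

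**The case against.** Ending charges at death is not in itself an error for a resource-use outcome, because no further hospital charges accrue. Death is reported as an outcome of its own. The QALY scale puts death at 0, the cost-benefit ratio in section 5.3.1 takes in outcomes as well as costs of care, and lethal vs non-lethal anomaly is a pre-specified subgroup. Controls may also receive postnatal sequencing (section 4.2.2), so redirected neonatal care is not confined to one group. Deaths after long intensive care can carry high charges. All of this stands, and it limits the point to the charge comparison and the NICU-stay comparison. It does not remove the point: none of these items changes how a death enters those two tests, and the subgroup is examined only after a significant group difference and a significant interaction.

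Four stronger readings are tempting, and the documents do not support them.

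- That the cost rule drops terminated pregnancies. The sentence in section 5.1 is about place of delivery. The rationale in the amendment log, that fetal deaths have no neonatal charges, is compatible with keeping them on maternal charges alone. What is missing is a clear statement.
- That omitted terminations always look like a benefit. The direction is open.
- That the false-positive rate is very large. A contrast such as 20% vs 10% mortality gives over 40%, but it needs more extra deaths than there are diagnosed infants.
- That ranking death worst restores a neutral test of stay. It does not: at 15% vs 10% with identical survivor stays, it declares the sequenced group worse in about 22% of trials. It answers a combined death/stay question.

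**Conclusion.** The gap is real and moderate. As written, an early death counts as a short, low-charge stay, and no planned analysis separates that from a benefit. For NICU stay the false rate is about 3-6% for a 1 to 2 point mortality excess and about 15% for 5 points (7% with later deaths), against 2.5%. For charges, a 2-5% excess of early deaths gives about 3-27% by log t-test, depending on how low the charges of those infants are. Termination can bias the charge comparison in either direction. These sizes rest on assumed mortality, timing of death and charge levels; the upper bound on plausible excess rests on the 9.4% planning yield. The documents do not show that sequencing raises mortality, and the point does not depend on it. The plan needs a rule that would let a reader tell the two explanations apart.

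**What to change.** 1. In section 5.3, analyse initial NICU stay as time to discharge alive with death as a competing event. Alternatively, use a death/stay composite with death ranked worst, declared as such. Report stay in infants discharged alive alongside either one.
2. In sections 5.1 and 5.3.1, report charges for (a) all pregnancies with known charges, where a fetal death or termination carries its actual maternal charges and zero neonatal charges, and (b) infants discharged alive.
3. Place counts of termination, fetal death and neonatal death by group next to any statement of cost saving.

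**Cost.** SAP wording and two extra tables. Death at discharge and delivery charges are already collected; any maternal charges for a termination enter only where known. No visits, patients or clinical rules change. The NICU summary becomes less simple than a median. The composite mixes death with stay, and the survivor analysis conditions on an event after exposure, so neither should be read alone.

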#### 4.10.3 Secondary Outcomes (Prenatal sequencing only)

- 10. Apparent prenatal phenotypic expansion from currently defined pediatric phenotypes
- 11. Variants of uncertain significance (VUS) that have not yet been associated with this disease phenotype
- 12. VUS subclassified as compelling variants in novel genes that are not yet disease associated (genes of uncertain clinical significance; GUS)
- 13. Pathogenic, likely pathogenic and VUS variants identified by sequencing (coding and non-coding regions) compared with coding regions only (digital WES)
- 14. Pathogenic, likely pathogenic and VUS variants identified by analysis of a proband alone compared to a proband-parent trio
- 15. Change in management decisions attributable to genomic results defined as changes to the patient's treatment plan or changes to the counseling of the patient/family regarding the immediate or long-term medical management
- 16. Accuracy of parental understanding of genetic test results
- 17. Educational/counseling and social support needs of the mother and father
- 18. Changes in classification of sequencing variants over time
- 19. Turnaround time of sequencing components and how it changes over time.

#### 5 Statistical Considerations

# 5.1 Power and sample size

The first primary outcome for this study is the frequency of pathogenic, likely pathogenic, or VUS genomic variants identified by sequencing among participants with a normal karyotype and CMA. The sample size is based on the incremental yield reported in a prospective study of WES performed at Columbia University in a similar population. Among 234 parent-fetus trios without CMA abnormalities, a genetic diagnosis was reported in 22 (9.4%). The precision of the estimate for a range of sample sizes and estimates is shown in Table 4. An estimate of 9.4% and sample size of 750 in the prenatal sequenced group will have a precision of 2.3% (confidence interval half-width) with a 93% probability.

Estimate	Sample size	Cl ½-width
9.0%	700	2.4%
	750	2.3%
	800	2.2%
9.4%	700	2.4%
	750	2.3%
	800	2.3%
9.8%	700	2.5%
	750	2.4%
	800	2.3%

The second primary outcome is maternal and neonatal hospital charges. The utilization of health care and cost only will include women that deliver at one of the study centers. Given that some of the recruiting centers include referrals in which the women will not deliver at the study center, power estimates assume cost will be available on 500 of the 750 in the prenatal sequencing group. Similarly, of the 350 unsequenced prenatal controls, 15% are assumed to have a pathogenic or likely pathogenic causal pre-/postnatal CMA prior to neonatal discharge or deliver elsewhere resulting in approximately 300 unsequenced prenatal controls available for analysis. The total charges for deliveries at Columbia University that required a NICU admission in 2016 and 2017 (partial year) were used to provide cost estimates. The charges follow a lognormal distribution approximately with a mean total charge of \$277,902 and standard deviation of \$389,484. Assuming 500 participants in the prenatal WGS group, and 300 unsequenced prenatal control participants, the study will have 80% power to detect a mean ratio of 0.80 (20% reduction) with an alpha=0.05 two-sided.

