# 5.2 Prenatal Sequencing Group Only

The primary and secondary outcomes for the sequencing variants are descriptive and will be reported as the observed proportion (frequency) with 95% confidence intervals. Exact confidence intervals will be reported as appropriate. Sequencing findings include variants or no variants (negative). Variants are further classified as pathogenic, likely pathogenic, or VUS. VUS is further categorized by whether the variants are in genes related to the fetal phenotype or known to cause severe childhood disease, or in a gene of uncertain significance (GUS). Sequencing findings will be reported overall, by single vs. multiple anomalies, by organ system (abdominal wall, CNS, face/ear, effusion, intrauterine fetal growth, GI tract, genitalia, heart, neck, renal tract, skeletal, spine, thorax), and by key demographics including maternal age, race/ethnicity and fetal sex. Pearson's chi-square or Fisher's Exact test for categorical variables and

Mann-Whitney U test for continuous outcomes will be used to assess associations by variant classification.

For each variant meeting the primary outcome definition (pathogenic, likely pathogenic, and uncertain genomic variants), the type of test that would identify the variant (WGS only, WES) will be determined centrally and used to report the incremental number of pathogenic, likely pathogenic, and VUS variants identified by WGS compared with WES.

Change in management decisions attributable to sequencing results are descriptive and will be reported as the frequency with 95% confidence intervals overall and by variant classification.

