#### **5.3.2** Psychosocial outcomes

The secondary psychosocial outcomes are descriptive and will be reported as the observed proportion (frequency) with 95% confidence intervals. Exact confidence intervals will be reported as appropriate. All outcomes will be assessed at three time periods (post disclosure/enrollment, post discharge, and 12 months postpartum) and each time period will be analyzed separately. The initial analyses will compare prenatal sequencing (those receiving a genetic result of any type) with the prospective unsequenced prenatal group. Exploratory analyses will include pairwise comparisons between each variant classification (unsequenced prenatal group, negative sequencing result, VUS result, and pathogenic/likely pathogenic sequencing results).

Associations between the outcomes and key demographics also will be assessed. Further, association between outcomes and study groups will be tested in a multivariate setting adjusting for other variables hypothesized to affect outcome (e.g. demographics, genetic essentialism and genetic optimism). Continuous outcomes will be analyzed using a multivariate linear regression model and binary outcomes using a logistic regression model. Standard model selection methods and regression diagnostics will be performed to assess goodness of fit.

A thematic analysis will be performed for the qualitative interview data to identify patterns or themes in these data. Summary statistics will be reported for the themes.

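### Does the 2.3-point precision in section 5.1 fail to cover the first primary outcome, which also counts reportable VUS?

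*Combined protocol and SAP*

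**What the plan says.** Protocol version 1.8, section 4.10.1, defines the first primary outcome as "Pathogenic, likely pathogenic, or VUS variants identified by sequencing and deemed reportable by the Variant Adjudication Committee". Section 5.1 restates it: "The first primary outcome for this study is the frequency of pathogenic, likely pathogenic, or VUS genomic variants identified by sequencing". Section 5.2 repeats the same three classes: "For each variant meeting the primary outcome definition (pathogenic, likely pathogenic, and uncertain genomic variants").

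For the size of the sequenced group, section 5.1 says "The sample size is based on the incremental yield reported in a prospective study of WES" and reports the source result: "Among 234 parent-fetus trios without CMA abnormalities, a genetic diagnosis was reported in 22 (9.4"%). It then gives the precision: "An estimate of 9.4% and sample size of 750 in the prenatal sequenced group will have a precision of 2.3% (confidence interval half-width"), with a probability of 93%. Table 4 extends this to rates of 9.0%, 9.4% and 9.8% and to sample sizes of 700, 750 and 800, at a probability of at least 90%.

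On analysis, section 5.2 says "The primary and secondary outcomes for the sequencing variants are descriptive". They are to be reported as proportions with 95% confidence intervals, exact where appropriate, and variants are broken down into pathogenic, likely pathogenic and VUS.

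**The concern.** The outcome is a composite of three classes, but the only rate used for sizing is described as a genetic diagnosis. A VUS on its own is not usually called a diagnosis. Elsewhere the protocol keeps the two apart: section 5.3.2 lists "negative sequencing result, VUS result, and pathogenic/likely pathogenic sequencing results" as separate groups, and Aim 4 in section 1.2 links diagnostic yield to pathogenic and likely pathogenic variants.

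If the 22 excluded VUS-only cases, the composite rate would exceed 9.4%. A proportion nearer 50% has a wider interval, so the 93% assurance would be too high for the outcome as defined. Table 4 stops 0.4 points above 9.4%, and no sequencing VUS rate appears anywhere in the documents. Precision is the only sample-size argument given for this outcome, so a reader could take 2.3 points as a design property that the composite does not have.

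**Working it through.** **Inputs.** n = 750, rate 22/234 = 0.094, half-width 0.023 and probability 0.93 come from section 5.1. The 95% level and the exact interval come from section 5.2. The composite rates above 9.8% used below are assumptions.

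**Method.** For each count x out of n, the exact (Clopper-Pearson) limits are

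- L(x) = Beta quantile at 0.025 with parameters (x, n − x + 1)
- U(x) = Beta quantile at 0.975 with parameters (x + 1, n − x)
- h(x) = [U(x) − L(x)]/2

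The assurance is P(h(X) ≤ 0.023) with X ~ Binomial(n, p).

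**Step 1: reproduce the plan's figure.** At n = 750 the largest count, on the low side of 50%, with h ≤ 0.023 is 82:

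- x = 82 (10.9%): h = 0.02299
- x = 83 (11.1%): h = 0.02311

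With p = 0.094, P(X ≤ 82) = 0.931, against the stated 93%. The half-width met with at least 90% probability is 0.02251, 0.02287 and 0.02323 at 9.0%, 9.4% and 9.8%. Rounded up to 0.1 point these are 2.3, 2.3 and 2.4, as in Table 4. The cells for n = 700 and n = 800 match as well, so there is no arithmetic error.

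**Step 2: see what a higher composite rate would do (n = 750).**

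| Assumed rate | P(half-width ≤ 2.3 points) | Expected half-width (points) | Half-width met with ≥ 90% probability (points, rounded up) |
|---|---|---|---|
| 9.4% | 93% | 2.15 | 2.3 |
| 10% | 82% | 2.21 | 2.4 |
| 12% | 20% | 2.39 | 2.6 |
| 15% | 0.07% | 2.62 | 2.8 |
| 20% | about 0 | 2.92 | 3.1 |
| 30% | about 0 | 3.34 | 3.5 |
| 40% | about 0 | 3.56 | 3.6 |

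The largest h(x) over all 751 possible counts is 0.0364, so the half-width is below 3.7 points whatever the rate.

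**Step 3: read the two scales correctly.** Suppose VUS-only cases add 3 points, giving 12.4% (0.03 × 750 = 22.5, about 23 more participants). The probability of meeting 2.3 points falls from 93% to 12%. Over the same step the expected half-width moves only from 2.15 to 2.42 points. The probability drops sharply because it counts crossings of one fixed threshold; the interval itself widens by about a quarter of a point. For example, an observed 90/750 (12.0%) would be reported with an exact interval of 9.8% to 14.5%.

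**Step 4: compare the texts on whether the 22 include VUS.**

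- For exclusion: the word diagnosis in section 5.1, Aim 4, and the separate grouping in section 5.3.2.
- For inclusion: section 5.1 names the composite, calls the earlier result an incremental yield and uses 9.4% as the estimate for this outcome. Aim 1a uses yield for all three classes together.
- Table 1 does not settle it. Its caption speaks only of pathogenic variants, and its column heading carries an asterisk with no footnote in the text available.

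Section 5.3.2 describes how this study groups its own results, not how the earlier study defined a diagnosis. The question stays open on the documents.

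**The case for a change.** The strongest case for a change is that a design statement about a primary outcome should describe that outcome. The 93% is sensitive to the rate: it falls to 90% at 9.6% and to 51% at 11%. A reportable-VUS share of one or two points (about 8 or 15 of 750) would bring it to 71% or 37%. The documents lean somewhat towards a diagnosis that excludes VUS. The repair would be cheap: check the source once, relabel one figure and add a few rows to Table 4.

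Part of this stands. Section 5.1 could say what the 22 covered, and it does not. The rest gives no reason to amend the plan. If the 22 included reportable VUS, the sentence is right as written. If they did not, it remains correct for the rate it names, and only the label is loose. Extra rows would rest on assumed rates, because the documents offer no sequencing VUS rate. Only reportable VUS count, and a participant with both a diagnosis and a VUS adds nothing to the composite. Section 1.3 requires Steering Committee and IRB approval for any protocol change, and here that would yield wording that alters no number in the final report.

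**Conclusion.** No change is needed. The 2.3 points with 93% probability is correct at 9.4%. Whether 9.4% is also a fair planning rate for the composite cannot be decided from the documents, because they do not define the genetic diagnosis in the source study.

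On the less favourable reading, the 90%-assurance half-width rises from 2.3 to 2.4, 2.6 or 2.8 points at assumed composite rates of 10%, 12% or 15%, with a ceiling below 3.7. The outcome has no hypothesis test or decision threshold, so the loss is one of planned precision alone. An analyst who follows section 5.2 will report the composite proportion with a valid 95% interval and will show pathogenic, likely pathogenic and VUS findings separately. Readers will therefore see both the achieved precision and the composition of the yield.

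This rests on exact intervals, 750 analysed participants and a composite rate that the documents leave unstated. Saying in section 5.1 what the 22 diagnoses covered would be a courtesy to readers if the protocol is reopened for another reason.
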